5.0 PATIENT ELIGIBILITY

Rev. 11/7/01 Each of the criteria in the following section must be met in order for a patient to be considered eligible for consolidation therapy and autologous stem cell transplantation.

Revised 8/7/00 a). Patients age \geq or equal to 16 and patients should have not reached their 61st birthday (physiological age 60).

b). Patients in first remission who are treated for acute myelogenous leukemia AML, FAB types, M0-M7. M3 will be excluded.

c). A marrow aspiration and biopsy demonstrating a complete hematological remission. Patients need to have a normal platelet count within five days of starting consolidation chemotherapy.

d). No cytogenetic abnormalities in the remission marrow.

Revised 11/19/02

Revised 3/11/02

- e). Patients who are in first complete remission of acute myelogenous leukemia who have received consolidation therapy prior to coming to transplant center will be eligible for the protocol but will be evaluated separately.
- f). Patients must be in complete remission for less than 6 months. Patients in remission for longer than 6 months may be placed on the study after review by P.I. and will be evaluated separately.

Exclusion Criteria:

1. Prior myeloproliferative disorder such as CML, myelofibrosis, essential thrombocythosis, or polycythemia vera.
2. Prior myelodysplasia or secondary leukemia.
3. Any severe chronic medical or psychological illness as in the judgment of the physician would jeopardize the ability of the patient to tolerate aggressive chemotherapy. Patients must have $FEV_1 > 60\%$ + $DLCO > 50\%$ a cardiac ejection fraction $\geq 50\%$ and creatinine clearance of $> 60 \text{ ml/min}$.
4. HIV positive
5. Pregnancy

Revised 3/11/02

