Autologous PSC Reinfusion: Side effects from the bone marrow and peripheral stem cell infusion should be minimal. Volume overload may be seen, but can be managed with diuretics. Fevers and chills may occasionally be encountered. At the University of Nebraska at least two patients developed acute abdominal pain of unknown cause during their marrow infusions. The pain was managed with narcotic analgesics and resolved spontaneously. The lysis of frozen erythrocytes may be associated with hemoglobinuria. Patients will have positive tests for blood in the urine, but no erythrocytes will be found in the sediment. At the University of Nebraska three patients developed acute renal failure after autologous bone marrow infusion. This problem was presumed to be due to hemoglobinuria and was no longer seen after red blood cells were removed from the marrow prior to cryopreservation. This is not expected to be a problem since we will also be removing the red cells with Ficoll-Hypaque. DMSO will be infused along with the bone marrow. It is excreted through the lungs and its characteristic odor may be noticeable for a few days after marrow infusion.

8.0 STATISTICAL CONSIDERATIONS:

8.1 Primary and Secondary Endpoints: The primary endpoints of this Phase II study are to evaluate the toxicity and efficacy of FTBI/VP-16 and targeted Busulfan dosage for AUC 700-900 as a preparative regimen for autologous BMT with primed peripheral stem cells following consolidation therapy with high dose Ara-c and idarubicin or high dose Ara-c alone in patients with AML in first complete remission (CR). Complete remission will be defined as neutrophils >1500/ml and platelets >100,000. Efficacy will be estimated as 2 and 5 year disease-free survival (DFS). The role of IL-2 following autologous BMT will also be evaluated based on feasibility of administration and ability to tolerate IL-2. The effect of cytogenetics, WBC at presentation, AUC of Busulfan and number of courses of induction therapy to achieve remission will be evaluated as possible prognostic factors for relapse, DFS, and overall survival.

8.2 Sample Size Estimation and Length of Accrual: A total of 50 patients with AML in first CR and less than \leq 60 years old will be accrued to this trial, so that in estimating the engraftment and relapse rates the maximum standard error will be 0.07. We expect to accrue approximately 10-12 patients per year so that this trial will require 4-5 years for completion.

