8.3 Statistical Analyses: The rate of engraftment and median time to engraftment will be estimated, defined as time to ANC>500 and platelets > 20,000.

The Kaplan-Meier method will be used to estimate time to relapse, DFS, and overall survival, and 95% confidence intervals will be calculated using Greenwold's variance. All patients receiving HD Ara-c and Idarubicin consolidation will be included in the analysis for intent-to-treat with autologous BMT. For overall survival, failure time will be calculated from the day of first consolidation treatment to the day of death due to any cause for those patients who fail. For DFS, the failure time will be calculated from the day of first treatment to the day of disease relapse or death due to any cause. For patients who remain alive and well at the time of analysis, the survival time will be censored as of the date of last contact.

A further analysis of time to relapse, DFS and overall survival will be carried out for the subset of patients who go on to autologous BMT, with survival estimates calculated from the day of transplant. The Cox proportional hazard regression model will be used to analyze possible prognostic factors for relapse, DFS and overall survival.

8.4 Early Stopping Rules: If at any time the severe treatment related complication rate (e.g. severe VOD, interstitial pneumonia, neurotoxicity at day 100 post ABMT), exceeds 10%, with a high probability (i.e. 95%) then further accrual to the trial will be terminated. Similarly if with a high probability (95%) the regimen related mortality at day 100 post ABMT exceeds 10% the trial will be terminated. This would occur if the following numbers of events have been observed, monitoring after every set of 10 patients it accrued:

Number of Patients Accrued	Number of Adverse Events Leading to Early Termination
10	4
20	5
30	7
40	8

Rev. 5/7/01

We will stop accrual of good risk cytogenetic patients on the study if the good risk cytogenetic patients demonstrate excess relapse. Based on previous COH experience, good risk cytogenetic patients have a relapse rate of 13%. The study will close if the lower bound of an estimate of the true rate of relapse exceeds 15% for the subgroup. Evidence of relapse will be taken as the lower limit associated with an exact 95% one-sided confidence interval for proportions. Table 1 below shows the critical points for early stopping of accrual.

Table 1: Critical points for early stopping for relapse

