9.0 WOMAN AND MINORITIES GUIDELINES

All eligible patients from both genders and from all racial/ethnic groups will be recruited equally into this trial, with the only exclusionary criteria being those stated in Section 5.0. Based on our patient population and previous experience with bone marrow transplantation for AML in first remission, the anticipated rates of entry into this study by gender and race/ethnicity are as follows:

Gender/Race/Ethnicity Table for Acute Myelogenous Leukemia Patients in First Complete Remission Transplanted at City of Hope National Medical Center

	American Indian or Alaskan Native	Asian or Pacific Islander	Black, not of Hispanic Origin	Hispanic	White, not of Hispanic Origin	Other or Unknown
Female	0%	12%	2%	16%	70%	0%
Male	0%	8%	2%	22%	65%	3%
Total	0%	10%	2%	19%	65%	2%

10.0 REGISTRATION GUIDELINES:

Revised 3/11/02

Once signed, informed consent has been obtained and all pretreatment evaluations have been performed, patients will be entered on study, after review of patient eligibility criteria by the assigned Clinical Research Associate (CRA) from City of Hope Department of Biostatistics. Patients may be screened for registration by calling the Department of Biostatistics, [name]. Eligibility checklists are attached. (Appendix IX). Patients will be taken off study at time of death.

11.0 DATA SUBMISSION SCHEDULE:

All primary data will be maintained by the assigned CRA from the Department of Biostatistics. Data will be collected by the CRA at the time of each patient evaluation. Records will be stored in a secure location within the Biostatistics Department.

Rev. 3/11/02

See Appendix VIII for time points for grading toxicities.

12.0 ETHICAL AND REGULATORY CONSIDERATIONS:

This study is to be approved by the Institutional Review Board according to City of Hope ethical and regulatory guidelines. All patients will have signed an informed consent for participation in research activities, and will have been given a copy of the Experimental Subject's Bill of Rights.

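### The day-100 stopping boundaries in 8.4 are exact only for transplanted patients with known day-100 status, but the table counts patients accrued

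*Combined protocol and SAP*

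**What the plan says.** Section 8.4 sets two limits that share one table. The mortality limit is tied to a time after transplant: "Similarly if with a high probability (95%) the regimen related mortality at day 100 post ABMT exceeds 10% the trial will be terminated". The complication limit is looser, because day 100 appears only among examples: "If at any time the severe treatment related complication rate (e.g. severe VOD, interstitial pneumonia, neurotoxicity at day 100 post ABMT". The table is presented as equivalent to these criteria ("This would occur if the following numbers of events have been observed, monitoring after every set of 10 patients it accrued"), with 4, 5, 7 and 8 events against 10, 20, 30 and 40 patients. Its first column counts patients accrued, a term that 8.4 does not define.

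Elsewhere, entry and transplant are different events:

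- Section 5.0 lists what a patient must meet to be "considered eligible for consolidation therapy and autologous stem cell transplantation".
- Section 10.0 fixes the moment of entry: "Once signed, informed consent has been obtained and all pretreatment evaluations have been performed, patients will be entered on study".
- Section 8.3 plans a separate analysis for "the subset of patients who go on to autologous BMT, with survival estimates calculated from the day of transplant".
- Section 3.0 reports two earlier series in which 44 of 60 and 50 of 58 intended patients were transplanted; ten of the 60 relapsed first.
- Section 8.2 gives the expected pace: "We expect to accrue approximately 10-12 patients per year".

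**The concern.** A patient who relapses before transplant, or was transplanted three weeks ago, has not yet contributed a day-100 outcome. Counting such patients in the denominator keeps the required number of events at a level meant for a larger evaluable group. The sentence and the table of one decision rule can then give different answers on the same data, and the table is the more lenient. At stake is the stopping limit for early mortality under a conditioning regimen in which intravenous busulfan replaces cyclophosphamide.

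**Working it through.** **Inputs.** Limit 10% and 95% probability (8.4); boundaries 4/5/7/8 (8.4); fractions transplanted 50/58 = 86.2% and 44/60 = 73.3% (3.0), assumed to apply here; accrual 10–12 per year (8.2). True rates of 10%, 20% and 30% are illustrative.

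**1. Reproducing the table.** Take the smallest r with P(X ≥ r | n, 0.10) ≤ 0.05, X binomial. This is the same as requiring the exact one-sided 95% lower limit to exceed 10%.

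| n | Printed r | Tail at r | Tail at r − 1 | Evaluable numbers, up to n, for which r is exact |
|---|---|---|---|---|
| 10 | 4 | 0.0128 | 0.070 | 9–10 |
| 20 | 5 | 0.0432 | 0.133 | 15–20 |
| 30 | 7 | 0.0258 | 0.073 | 28–30 |
| 40 | 8 | 0.0419 | 0.0995 | 35–40 |

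All four boundaries reproduce when n is fully evaluable. Two-sided exact limits, uniform-prior and Jeffreys Bayes, Wald and score rules each fail on at least one row. The method is therefore clear, and the boundaries themselves are right.

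**2. Effect of entrants who are not transplanted.** The exact boundary is 3 for 4–8 evaluable patients, 4 for 9–14, 5 for 15–20, 6 for 21–27, 7 for 28–34 and 8 for 35–41.

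| Accrued | Expected transplanted, 86% / 73% | Chance that the exact boundary is below the printed one, 86% / 73% |
|---|---|---|
| 10 | 8.6 / 7.3 | 41% / 79% |
| 20 | 17.2 / 14.7 | 5% / 45% |
| 30 | 25.9 / 22.0 | 80% / 99% |
| 40 | 34.5 / 29.3 | 48% / 97% |

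Examples:

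- 30 accrued, 26 transplanted, 6 events: tail 0.040, lower limit 10.6%. The criterion is met; the table asks for 7.
- 40 accrued, 34 transplanted, 7 events: tail 0.048, lower limit 10.1%. The criterion is met; the table asks for 8.

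**3. Over the four looks.** Exact recursion over numbers transplanted and events, with no follow-up lag:

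| True rate | Table stops, all evaluable | Table stops, 86% / 73% | Criterion met at a look but table never stops, 86% / 73% |
|---|---|---|---|
| 10% | 7.3% | 4.0% / 2.0% | 2.6% / 4.3% |
| 20% | 62% | 45% / 29% | 9.3% / 19.6% |
| 30% | 95% | 87% / 72% | 4.4% / 14.7% |

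The reverse case, a table stop without the criterion being met, has probability 0.

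**4. If accrued means transplanted.** Attrition drops out, but nothing requires the counted patients to have reached day 100. Suppose looks are taken at the instant of accrual. The tenth patient is then pending, and so are on average 10 × 100/365 = 2.7 to 12 × 100/365 = 3.3 of the others. That leaves 10 − 1 − 2.7 = 6.3 down to 10 − 1 − 3.3 = 5.7 of the first ten past day 100. Simulation with Poisson accrual and events uniform over days 0–100 gives a 52–53% chance of stopping at a true 20% rate, against 62% with full follow-up.

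**The case against.** The strongest reply is that accrued was meant as transplanted. Section 8.2 sizes the trial at 50 accrued "so that in estimating the engraftment and relapse rates the maximum standard error will be 0.07". √(0.25/50) = 0.0707, so for engraftment, which exists only after transplant, that figure needs 50 transplanted patients. With 50 × 0.862 ≈ 43 or 50 × 0.733 ≈ 37 transplanted, it would be 0.076 or 0.082. The exact match of 4/5/7/8 points the same way. This stands as a possible reading. On it, every attrition figure falls away and only step 4 remains, with a size that depends on when looks are taken. It does not settle the matter, because 8.3, 5.0 and 10.0 point to entry before transplant.

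Other objections stand in part:

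- The complication limit may cover consolidation events, for which all entered patients are a possible denominator.
- The 73% series is older and used another conditioning regimen. The 86% series was still running, so some of its patients may have been awaiting transplant. Entrants consolidated elsewhere may raise the fraction.
- At 86% the expected numbers leave the 10 and 20 rows unchanged.
- A monitor may apply the written criterion directly, since 8.4 says it holds at any time. That avoids the missed stop but confirms that text and table disagree.

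A reader might infer that the boundaries are miscalculated, that every row is wrong, or that the trial has no other safeguard on early deaths. The documents support none of these. The boundaries are exact for evaluable patients, and the binomial steps leave slack in each row. Section 13.0 provides for committee review of serious adverse events. Appendices VII and VIII, to which it refers, were not available to check for further limits or evaluability rules.

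**Conclusion.** The mismatch is real: the criterion concerns day-100 outcomes after transplant, while the table's denominator is an undefined accrual count. If accrued means entered, the silent cases amount to 9.3% or 19.6% of trials at a true 20% rate, assuming the earlier-series fractions, no lag, and looks at exactly 10, 20, 30 and 40. If it means transplanted, the loss is smaller: about 9 to 10 percentage points of stopping probability under the step 4 assumptions, and less if looks wait for follow-up. Both errors run towards missed or late stops, and neither adds false stops. Severity is minor to moderate.

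**What to change.** In 8.4:

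1. Relabel the first column as patients transplanted and evaluable to day 100. Take looks at the first 10, 20, 30 and 40 consecutive such patients, and keep 4/5/7/8.
2. Declare a boundary crossed as soon as its count is reached within a cohort. Pending patients can only add events, so this anticipates a stop that the completed cohort would give.
3. State that the criterion is assessed at these looks, so that text and table agree.
4. State whether events before transplant count for the complication limit and, if so, over which patients.

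Item 2 is essential. Over the first 40 accrued at a true 20% rate and 86% transplanted, relabelling with complete looks only moves the chance of stopping from 45% to 47.6%, and the silent cases from 9.3% to 8.5%. With the early call these become 51.5% and 4.5%. At 73%, the early call gives 45% instead of 29%, and silent cases fall from 19.6% to 5.3%. The false-stop rate at a true 10% stays at or below the designed 7.3%.

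The repair does not flag every case. Six events in 26, or seven in 34, fall between looks and may still not stop accrual, which is why item 3 is needed. Testing after every patient would raise the false-stop rate to 9.8% if started at the 10th patient and 12.4% if started at the first.

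The cost is a few sentences and one column label, with no added patients or procedures. Complete looks come later: the median first one is at about 17.5 months (86%) or 19.6 months (73%), against 10.6 months at the tenth accrual, assuming 11 entries a year and 60 days from entry to transplant. The early call reduces that delay. Forty transplants are reached within 50 accrued in only 92% or 18% of trials, so the last look may not take place.

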9.0 WOMAN AND MINORITIES GUIDELINES

All eligible patients from both genders and from all racial/ethnic groups will be recruited equally into this trial, with the only exclusionary criteria being those stated in Section 5.0. Based on our patient population and previous experience with bone marrow transplantation for AML in first remission, the anticipated rates of entry into this study by gender and race/ethnicity are as follows:

Gender/Race/Ethnicity Table for Acute Myelogenous Leukemia Patients in First Complete Remission Transplanted at City of Hope National Medical Center

	American Indian or Alaskan Native	Asian or Pacific Islander	Black, not of Hispanic Origin	Hispanic	White, not of Hispanic Origin	Other or Unknown
Female	0%	12%	2%	16%	70%	0%
Male	0%	8%	2%	22%	65%	3%
Total	0%	10%	2%	19%	65%	2%

10.0 REGISTRATION GUIDELINES:

Revised 3/11/02

Once signed, informed consent has been obtained and all pretreatment evaluations have been performed, patients will be entered on study, after review of patient eligibility criteria by the assigned Clinical Research Associate (CRA) from City of Hope Department of Biostatistics. Patients may be screened for registration by calling the Department of Biostatistics, [name]. Eligibility checklists are attached. (Appendix IX). Patients will be taken off study at time of death.

11.0 DATA SUBMISSION SCHEDULE:

All primary data will be maintained by the assigned CRA from the Department of Biostatistics. Data will be collected by the CRA at the time of each patient evaluation. Records will be stored in a secure location within the Biostatistics Department.

Rev. 3/11/02

See Appendix VIII for time points for grading toxicities.

12.0 ETHICAL AND REGULATORY CONSIDERATIONS:

This study is to be approved by the Institutional Review Board according to City of Hope ethical and regulatory guidelines. All patients will have signed an informed consent for participation in research activities, and will have been given a copy of the Experimental Subject's Bill of Rights.

When results of this study are reported in medical journals or at meeting, identification of those taking part will be withheld. Medical Records of patients will be maintained in strictest confidence, according to current legal requirements. However, they will be made available for review, as required by the Food and Drug Administration (FDA) or other authorized users such as the National Cancer Institute (NCI), under the guidelines established by the Federal Privacy Act.

13.0 Data & Safety Monitoring Plan (See Appendix VII)

Toxicities will be graded using the Common Toxicity Criteria 2.0 published date April 30, 1999, Appendix VI [special attention to BMT section].

Frequency for grading and recording toxicities, see Appendix VIII.

- i. The COH IRB and the Clinical Protocol Review Monitoring Committee (CPRMC) and Data Safety Monitoring Board (DSMB) will have the data monitoring oversight responsibilities. The COH has an NCI approved clinical monitoring plan. The CPRMC is an NCI approved clinical trials monitoring committee. The COH IRB meets twice monthly and reviews protocols annually. The CPRMC meets twice per month. Monitoring accrual and SAE's will be performed by that committee. Adverse events will be reported to the COH IRB and CPRMC [DSMB].\
- ii. Guidelines for reporting AE's and ADRS – See Appendix VII.

Appendix I

IV BUSULFAN KINETICS FORM

IRB#: _____

DATE: _____

PATIENT _____

DOSE # _____ Actual Body Weight _____

Medical Record # _____

Start time: _____ Stop time: _____

Date of birth: _____

DOSE: _____ mg

Social Security#: _____

MD/Pager#: _____ Coordinator/Pager # _____

INFUSION TO RUN OVER 2 HOURS

Tube #	Collection Schedule	Proposed Collection Time	Actual Collection Time
1	Immediately prior to beginning of infusion	APPROX. 0555	
2	Immediately prior to end of infusion	APPROX. 0755	
3	15 minutes post infusion	APPROX. 0815	
4	30 minutes post infusion	APPROX. 0830	
5	60 minutes post infusion (1 hour)	APPROX. 0900	
6	180 minutes post infusion (3 hours)	APPROX. 1100	
7	240 minutes post infusion (4 hours)	APPROX. 1200	

** ALL samples to be obtained in 7cc green top tubes (Sodium Heparin) and kept on ice at Nurses Station.

Then send to Clinical Pathology.

RN SIGNATURE _____

Ship on 5kg dry ice.

Results will be reported to the attending physician page by 4 p.m. Pacific time.

Revised 3/11/02

Results will also be faxed.

Appendix II
COH Schema

Session	Day	Time	Beam Direction	Energy (MeV)	Dose (cGy)	Notes
1	-6	0730	AP	8/10X	120	TLD
2	-6	1230	PA	8/10X	120	
3	-6	1730	AP	8/10X	120	
				8/10X	120x	
4	-5	0730	PA	e^- boost	300 e^-	Chest-wall boost
				8/10X	120x	
5	-5	1230	AP	e^- boost	300 e^-	need not be given
				8/10X	120X	
6	-5	1730	PA	e^- boost	300 e^-	in successive fractions
				8/10X	120X	
7	-4	0730	AP	e^- boost	300 e^-	
8	-4	1230	PA	8/10X	120	
9	-4	1730	AP	8/10X	120	
10	-3	0730	PA	8/10X	120	

Appendix IIa

University of Wisconsin Hospital and Clinical TBI Schema BMT 2001-403 UWHC IRB# 99040

Session	Day	Time	Beam Direction	Energy (MeV)	Dose (cGy)	Notes
1	-6	0730	AP	8/10X	150X	TLD
2	-6	1700	PA	8/10X	150X	
3	-5	0730	AP	8/10X e ⁻ boost	150X, 300 e ⁻	
4	-5	1700	PA	8/10X e ⁻ boost	150X, 300 e ⁻	
5	-4	0730	AP	8/10X e ⁻ boost	150X, 300 e ⁻	
6	-4	1700	PA	8/10X e ⁻ boost	150X, 300 e ⁻	
7	-3	0730	AP	8/10X	150X	
8	-3	1700	PA	8/10X	150X	

Electron beam set so the 90% PDD fails at the pleura.

2/26/02 written by [name], Physicist
Department of Radiation Oncology
University of Wisconsin Hospital and Clinics

Appendix III

Consolidation therapy (All testing to be completed no more than 4 weeks prior to starting treatment)

Required studies	Pre study	Day 1	Day 2	Day 3	Day 4	Day 5	Day 6	Day 7	Day 8	Day 9	Day 10	Day 11	Day 12	Day 15	Until PBSC
BM asp, biopsy	X														
Cytogenetics	X														
HIV	X														
CBC,Diff, PLT **	X	X	X	X	X	X	X	X	X	X	X	X	X	X	
CMP, uric acid, phosphorous, LDH ++	X	X		X		X		X		X					
Magnesium ++	X	X		X		X		X		X		X		X	
UA	X														
24hr Crea cl	X														
Hepatitis panel	X														
Herpes simplex titer	X														
CMV titer	X														
Immunoglobulin levels	X														
Thyroid panel	X														
CXR	X														
LP*	X														
ECHO or MUGA	X														
CT scan Chest, ABD, Pelvis	X														
PFT	X														
HLA Typing of patient and sibling	X														
Pregnancy	X														
Cholesterol	X														
TREATMENT															
Consolidation															
HD ARA-C		X	X	X	X										
Idarubicin***		X	X	X											
GCSF#													X	X	X

*Lumbar Puncture will be performed in patients with FAB M4, M4eo, M5, and patients with WBC at diagnosis >50,000 and patients with cutaneous involvement 12 mg of intrathecal methotrexate should be given at the time of the LP.

GCSF will be given until stem cells are collected

++ Comprehensive Metabolic Panel plus uric acid, phosphorous and LDH every Monday, Wednesday, Friday during consolidation

** CBC, Diff, PLT should be done until ANC >1500 and PLTs >150. Diff. to be done on admission and then when WBC recovers to >500.

***Give Idarubicin dose after Ara-C dose 1,3 and 5.

See section 6.1 for exceptions.

++Comprehensive Metabolic Panel [See appendix X for tests included].

